#### 4.6. Rationale for benefit-risk ratio

Cardiac arrest is a highly critical medical emergency. Only approximately 1/3 of all patients with VT/VF will survive to 30 days with standard ACLS treatment. Patients that survive the initial resuscitation phase and are transferred to hospital may still suffer from anoxic brain injury, cardiogenic shock, multiorgan failure and traumatic injuries from chest compressions. It is therefore of highly importance to as soon as possible convert patients in VF/VT to sustain circulation

In cardiac arrest situation with VT / VF early defibrillation within 3-5 minutes is the most important therapeutic treatment to terminate the arrythmia and based on the results from previous trials there is a strong signal that DSD is superior to standard defibrillation in refractory VT/VF. In terms of survival. The risks with DSD includes a theoretical risk of defibrillation damage but this risk appears to be exceedingly low. Another physical risk is worse CPR quality. However, to be in a cardiac arrest is highly time critical, and every minute that passes without restoration of spontaneous circulation is associated with lower survival. Part of this is due to irreversible brain damage that is caused by cerebral hypoperfusion during the cardiac arrest. The earlier VT/VF can be terminated, and spontaneous circulation be restored, the higher the probability of survival. We believe that a DSD strategy a soon as possible can have a potential dual positive effect since

- a) a larger proportion of patients will have their VT/VF terminated and spontaneous circulation restored, e.g. higher survival
- b) the termination of VT/VF will occur sooner, leading to shorter duration of brain hypoperfusion and ischemia, e.g. better neurological function among survivors.

Version No: 1.1

Date: 2024-10-27 24 (48)

In summary we believe that this novel method to use defibrillators have a strong potential benefit that largely outweighs the potential risk, and that the intervention can have a direct positive effect on the study participants. The net benefit is likely to be determined by efficacy of the intervention rather than safety aspects.

## 5. Objectives and hypotheses of the clinical investigation

## 5.1. Objectives

## 5.2.1. **Primary objective**

The overall aim of this pilot study is to evaluate feasibility of a Randomized Controlled Trial comparing a strategy with DSD defibrillation as soon as possible to standard defibrillation in OHCA patients who remain in VT/VF after the first shock.

## 5.2.2. Secondary objective(s)

To obtain data to inform design of the planned main study that will assess clinical outcomes

## 5.2.3. Safety objectives

To asses safety of an early DSD strategy in terms of CPR quality and defibrillation performance.

## 5.2. Hypotheses

## 5.3.1. **Primary hypothesis**

Randomization to a strategy of either early DSD or standard defibrillation is feasible and safe in terms of timely randomization, adherence to protocol, maintained CPR quality and defibrillation functionality.

## 6. Design of the clinical investigation

#### 6.1. General information

**Design:** This is an academic, investigator initiated, open-label pilot study with a randomized controlled trial (RCT) design and 3:1 allocation (3 DSD: 1 standard). Screening for inclusion will be performed in all cardiac arrests by participating EMS units where there are two study-specific defibrillators available on site (One (1) Corpuls3 + one (1) Corpuls3 *or* one (1) Corpuls1).

**Study population:** All adult OHCA patients (≥18 years) with VT/VF at rhythm analysis after the first defibrillation.

Version No: 1.1

Date: 2024-10-27 25 (48)

**Study setting:** The study is conducted in the prehospital emergency medical services, i.e. ambulance organizations. The trial will be conducted by participating ambulance units attending OHCA's staffed with special nurses. These units will perform screening for inclusion, randomization, intervention or control treatment and initial follow-up. All ambulance units in Sweden follow European resuscitation council (ERC) guidelines published in 2021 [4] and perform team training on an annual basis for high quality provision of ACLS care in OHCA.

## 6.2. Endpoints

#### 6.2.1. Primary endpoints

**The main feasibility endpoint** is the proportion of included patients randomized before three EMS defibrillations.

In order to perform early DSD inclusion and randomization has to be quick, therefore the total number of EMS defibrillations prior to randomization was chosen as the main feasibility outcome. The goal is to perform randomization as soon as possible, however in clinical practice this can be challenging. A target of above 80% of included patients randomized before three EMS defibrillations is deemed acceptable. Other feasibility objectives will evaluate cross-over.

The main safety endpoints are related to CPR quality defined as chest compression fraction and any defibrillation malfunction defined as inability to defibrillate or any other defibrillator device deficiency (DD).

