**Study rationale:** In order to evaluate if an early DSD-strategy could benefit all patients with VT/VF after the first shock, including those not in refractory VF the Double D trial is designed. The first phase of the Double D trial is a pilot-study assessing feasibility and defibrillation safety, presented here. If DSD would prove to be superior to standard defibrillation in a broader cardiac arrest population, also among those not in refractory VF, this would have a large impact on how Advanced Cardiac Life Support (ACLS) should be performed.

**Design:** This is an academic, investigator initiated, openlabel pilot study with a randomized controlled trial (RCT) design and 3:1 allocation (3 DSD: 1 standard). Screening for inclusion will be performed in all cardiac arrests by participating EMS units where there are two study-specific defibrillators available on site (One (1) Corpuls3 + one (1) Corpuls3).

**Study population:** All OHCA patients (≥18 years) with VT/VF at rhythm analysis, at least one defibrillation performed in standard A-L position.

**P:** Adult patients, 18 years or older, with OHCA and a shockable rhythm (VT/VF) after ambulance arrival and at least one defibrillation in standard position

**I:** Application of a second defibrillator with pad-placement in the anterior-posterior (A-P) position as early as possible after the first shock and a double sequential defibrillation in the following rhythm analysis phase if the patient is still in VT/VF

**C:** Standard defibrillation electrode placement (A-L)

**O**: Assessment of feasibility in terms of inclusion, time to inclusion and randomization, adherence to protocol and safety in terms of adverse events and CPR quality.

The pilot study is conducted in the prehospital emergency medical services, i.e. ambulance organizations primary in Alingsås/Kungälv, Sahlgrenska, Gothenburg and Region Halland. Other areas/regions can be allocated later.

Version No: 1.1

Date: 2024-10-27 11 (48)

	The trial will be conducted by participating ambulance units attending OHCA's. These units will perform screening for inclusion, randomization, intervention or control treatment and initial follow up.
Investigational device:	Corpuls3
Number of subjects:	40
Inclusion criteria:	- OHCA patients with VT/VF and at least one (1) defibrillation performed in standard (A-L) position

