Exclusion criteria:	

- Age < 18 years

- Obvious pregnancy

- Known preexisting Do Not Attempt Resuscitation order

Study objectives:	Primary objective: To evaluate feasibility and defibrillation safety in a randomized pilot trial, comparing the effect of a double defibrillation strategy, initiated as soon as possible after the first shock has been delivered, among all patients with Out of Hospital Cardiac arrest (OHCA) remaining in a shockable rhythm (VT/VF) after the first defibrillation. The results from this pilot trial will inform design of a larger multicenter survival study.
	Secondary objective: To provide a power-calculation for a larger survival study
	Safety objective: To asses safety of an early DSD strategy in terms of CPR quality and defibrillation performance.
Study endpoints:	Primary endpoints are defined as feasibility and safety measures as described below:
	Feasibility:  - Number of EMS defibrillations prior to randomization (target > 80% before third defibrillation)  - Among patients randomized to DSD, proportion that received DSD (target > 80%)  - Among patients randomized to standard, proportion that received DSD (target < 10%)

Version No: 1.1

Date: 2024-10-27 12 (48)

- Proportion of eligible patients included and randomized (target > 80%)

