#### Feasibility:

- Number of EMS defibrillations prior to randomization (target > 80% before third defibrillation)
- Among patients randomized to DSD still in VF in the following rhythm analysis, proportion that received DSD (target > 80%)
- Among patients randomized to standard, proportion that received DSD (target < 10%)

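### The synopsis and section 6.2.1 state the primary feasibility endpoints in two incompatible ways: the eligible-patient target is in one list only, and the denominators for DSD received differ

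*Protocol*

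**What the plan says.** The synopsis treats all its feasibility and safety measures as primary and lists four for feasibility. Two of them matter here:

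- DSD received: "Among patients randomized to DSD, proportion that received DSD (target > 80", in per cent.
- Recruitment: "Proportion of eligible patients included and randomized (target > 80", in per cent.

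The synopsis also describes the outcome as "Assessment of feasibility in terms of inclusion, time to inclusion and randomization", and says of the pilot's purpose: "The results from this pilot trial will inform design of a larger multicenter survival study".

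Section 6.2.1 opens with the main feasibility endpoint, which "is the proportion of included patients randomized before three EMS defibrillations". It then says: "Other feasibility objectives will evaluate cross-over". Its list has three measures. The recruitment proportion is absent, and DSD received becomes "Among patients randomized to DSD still in VF in the following rhythm analysis, proportion that received DSD (target > 80", again in per cent.

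The intervention itself is conditional. The synopsis calls for "a double sequential defibrillation in the following rhythm analysis phase if the patient is still in VT/VF", and section 2.2 (Performing DSD within the Double-D trial) makes the same condition.

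**The concern.** A pilot with no hypothesis test is judged mainly against its stated feasibility targets. Here two of those targets depend on which page is read. One primary measure appears in the synopsis only. Another has the same target in both places but a different denominator.

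The synopsis denominator for DSD received also has a fault of its own. It includes patients who left VT/VF after randomization and so, under the protocol's own rule, were not due DSD. They count as failures of delivery although the crew followed the protocol.

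At stake is what the pilot may report. If the wording is settled only after the data are seen, the more favourable list can be chosen, and the delivery estimate passed to the main trial changes with that choice.

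**Working it through.** **Arm sizes.** 40 patients at 3:1 give 40 × 3/4 = 30 and 40 × 1/4 = 10, as section 6.3.3 states. The protocol makes no power calculation (section 7.4), so there is no other figure to reproduce.

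**The two lists side by side.**

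| Measure | Target | Synopsis | Section 6.2.1 |
|---|---|---|---|
| Randomized before the third EMS defibrillation | > 80% | listed | listed, and named as main |
| DSD received | > 80% | of all randomized to DSD | of those randomized to DSD and still in VF at the next analysis |
| DSD received in the control arm | < 10% | listed | listed |
| Eligible patients included and randomized | > 80% | listed | absent |

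The first and third rows agree. The second and fourth do not.

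**DSD received.** The planned DSD arm has n = 30. The smallest count above 80% of 30 is 25 (25/30 = 83.3%), because 24/30 = 80.0% does not exceed the target. Assume that k patients are never shockable again and get no DSD, and that all others are in VF at the next analysis and get it. The synopsis proportion is (30 − k)/30, and the section 6.2.1 proportion is (30 − k)/(30 − k). The protocol gives no value for k.

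| k (assumed) | Synopsis | Section 6.2.1 |
|---|---|---|
| 5 | 25/30 = 83.3%, met | 25/25 = 100%, met |
| 6 | 24/30 = 80.0%, missed | 24/24 = 100%, met |
| 10 | 20/30 = 66.7%, missed | 20/20 = 100%, met |

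From k = 6 upward the synopsis target cannot be reached even with perfect adherence.

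Now assume instead that DSD is delivered to 95% of those still in VF, and let c be the share no longer in VF. For the synopsis, X is binomial (30, 0.95 × (1 − c)) and the target needs X ≥ 25. For section 6.2.1, the denominator is 30 × (1 − c), and the target needs the smallest count above 80% of it.

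| c (assumed) | Chance of meeting the synopsis target | Needed under 6.2.1 | Chance of meeting the 6.2.1 target |
|---|---|---|---|
| 0% | 0.997 | 25/30 | 0.997 |
| 10% | 0.738 | 22/27 | 0.998 |
| 20% | 0.240 | 20/24 | 0.994 |
| 30% | 0.034 | 17/21 | 0.997 |

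**Section 6.2.1 is not clean either.** It says VF, where the synopsis and section 2.2 say VT/VF. It also looks only at the next rhythm analysis, whereas sections 2.2 and 6.6 (Intervention) apply DSD to later shocks as well. A patient who is not shockable at the next analysis but becomes so afterwards falls outside its denominator.

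**Eligible patients.** With E eligible and all 40 randomized patients truly eligible, the target needs 40/E > 0.80, that is E < 50. So 40/49 = 81.6% meets it and 40/50 = 80.0% does not; 60 eligible give 66.7% and 80 give 50.0%. E is an assumption. Section 7.1 foresees that some randomized patients will prove ineligible. If 38 of the 40 were eligible, 38/47 = 80.9% meets the target and 38/48 = 79.2% does not. Section 6.2.1 sets no such test. Its three measures are all counted within included patients, and enrolment runs until 40 are included (section 7.4), so they can be met however many eligible patients were missed.

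**The case against.** The strongest reply is that little depends on the difference. The main endpoint and its target are the same in both places, as is the control cross-over measure. Section 7.4 rules out hypothesis testing, and no stop or go decision is tied to any target. Every contrast between met and missed above uses an assumed count. Removing the recruitment measure from the synopsis would be as consistent as restoring it, because the primary hypothesis in section 5.3.1 does not name inclusion. All of this stands. It limits the weight of the point but does not make the two lists agree.

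A reader might infer three stronger things that the protocol does not support:

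- **That the recruitment target has been abandoned.** The synopsis still states it, so the position is unclear rather than settled.
- **That the eligibility rules contradict each other.** Section 6.1 asks for VT/VF after the first defibrillation. Section 6.3.1 can be read the same way, as VT/VF at an analysis after both ambulance arrival and at least one shock. The wording is ambiguous. Aligning it would not by itself fix who is eligible, since the need for two study defibrillators on site (section 6.6) is missing from the criteria in sections 6.3.1 and 6.3.2.
- **That the section 6.2.1 denominator is right as it stands.** It leaves out VT and patients who become shockable later.

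**Conclusion.** The point holds as an internal inconsistency in the primary feasibility endpoints. One measure is primary in the synopsis and absent from section 6.2.1, and one shared measure has two denominators under the same target. The synopsis denominator is also wrong on the protocol's own terms, because it counts patients who were not due DSD as failures.

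The gap can decide the result. It does so from 6 non-shockable patients among the planned 30 for DSD received, and from 50 eligible patients against 40 randomized for recruitment. Both thresholds rest on assumed counts and on otherwise perfect delivery or eligibility. The inconsistency itself rests on neither. The harm is confined to reporting: the same data can be presented as meeting or missing a primary feasibility target. It should be corrected, but it does not threaten the main endpoint.

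**What to change.** Before results are known, make the synopsis and section 6.2.1 agree.

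1. **DSD received.** Use one denominator in both places: patients randomized to DSD who have VT/VF, not only VF, at a rhythm analysis after randomization. Say whether that means the next analysis or any later one. Report the proportion of all patients randomized to DSD beside it.
2. **Eligible patients randomized.** Either restore this measure and its target to section 6.2.1 or delete it from the synopsis. Restoring it is preferable, because the synopsis names inclusion as a feasibility outcome and no other measure has an eligible-patient denominator. The sponsor should confirm which is meant.
3. **If it is kept, define eligible once.** Cover both the rhythm wording (sections 6.1 and 6.3.1) and the two-defibrillator prerequisite (section 6.6). Patients who were eligible but not randomized could be counted from the resuscitation register part 1, ambulance charts and dispatch data (section 8.1). This route is optional. The prehospital CRF1 cannot supply these patients, since it is opened from the randomization sheet.

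The cost is wording, plus approval under section 9 if the change counts as a substantial modification. Keeping the eligible-patient measure may add one data extraction, which the approvals would have to cover, and the reported inclusion proportion may look less favourable.

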#### Feasibility:

- Number of EMS defibrillations prior to randomization (target > 80% before third defibrillation)
- Among patients randomized to DSD still in VF in the following rhythm analysis, proportion that received DSD (target > 80%)
- Among patients randomized to standard, proportion that received DSD (target < 10%)

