#### Performing DSD within the Double-D trial:

In this trial all patients will be connected to corpuls3 with electrodes in standard A - L electrode position.

If another defibrillator (AED) is already attached to the patient at EMS arrival the EMS will remove the electrodes from the other defibrillator and attach cor-patch electrodes in standard A-L position and connect them to corpuls3 in all cases. This is all part of current routine practice.

If randomized to intervention, electrodes from a second defibrillator (corpuls3 or corpuls1) are placed in the anterior-posterior position during interruptions in chest compressions for ventilation, thus not interfering with the electrodes from the first defibrillator. Attachment of the second defibrillator electrodes shall be made as soon as possible after randomization.

Version No: 1.1

Date: 2024-10-27 17 (48)

If the patient has VT/VF at the subsequent rhythm analysis (every two minutes during CPR) both defibrillators are charged simultaneously during chest compressions and shocks from the two defibrillators are delivered with approximately 1 second delay from each other (A-L first, A -P second when possible) and CPR immediately resumed (DSD strategy). For all consecutive defibrillations a DSD strategy will be used if the patient remains in VT/VF, termination of resuscitation or decision to transfer the patient to hospital. The total shock pause (hands off interval where no compressions are performed) is recommended to be less than 5 seconds.

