#### Intervention

If the patient is randomized to the intervention group, the ambulance crew team will apply the second defibrillator with electrodes placed in the A-P position as soon as possible. Defibrillation is performed by one person defibrillating both defibrillators in a sequential manner "Double Sequential Defibrillation" (DSD). All consecutive defibrillations will thereafter be performed with the DSD strategy until ROSC, termination of resuscitation or decision to move the patient to hospital.

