## 7.4. Sample size calculation

No power or sample size calculation will be made in the pilot phase. The main reason is that it is a feasibility pilot study and no hypothesis testing will be performed.

The main purpose of the pilot study is to determine timely inclusion and randomization, measure adherence to protocol and assess safety aspects. The pilot study will also try to identify potential obstacles in conducting the study so they can be resolved prior to the main study.

The pilot phase of the study will continue until 40 patients (3:1 randomization) are included. The results from the pilot study will be of importance and used to inform a sample size calculation in a planned main study.

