#### 8.1 Prehospital CRF1, Characteristics during the resuscitation phase

After completing the care of the patient, the study responsible EMS-unit will report a digital prehospital CRF. This is practically done by using and reading a study specific QR-code located on the back of the specific randomization envelope / sheet using a smart-phone. This will open a webpage automatic registration of time of registration and information to be filled in when opened.

Version No: 1.1

Date: 2024-10-27 33 (48)

The prehospital CRF will contain basic on-site information such as which ambulance that performed randomization, randomization study number, time and date of cardiac arrest, number of shocks prior to EMS arrival and number of shocks prior to randomization, treatment allocation, electrode placement for each defibrillation, number of defibrillations before DSD, ROSC and if the patients survived the event. Furthermore, if the patient has a known identity, personal id-number will be included to enable follow up. If the patients do not have a known identity a temporary identification number will be used.

The prehospital CRF allows for real-time monitoring of randomization and allows for early start of follow-up.

Other core resuscitation characteristics will later be reported and collected from the SRCR part 1 and ambulance charts. This registry data is standard and mandatory for all EMS personal to report and contains resuscitation and patient characteristics and reporting to the register is part of routine documentation.

ECG files from defibrillators. All data stored in the defibrillators after each use in the trial will be exported to a secure server and analyzed for defibrillation safety and CPR quality.

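### The DSD-arm adherence endpoint shows whether DSD was given, not whether it was sustained over later VT/VF shocks as the strategy requires

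*Protocol*

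**What the plan says.** **The strategy.** Section 2.2 (Performing DSD within the Double-D trial) states: "For all consecutive defibrillations a DSD strategy will be used if the patient remains in VT/VF". Section 6.6 (Intervention) agrees: "All consecutive defibrillations will thereafter be performed with the DSD strategy until ROSC", with the end of resuscitation or a decision to transport as the other end points.

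**The endpoint.** Section 6.2.1 (Feasibility) gives one adherence measure for the DSD arm: "Among patients randomized to DSD still in VF in the following rhythm analysis, proportion that received DSD (target > 80" (per cent). The Synopsis has the same numerator and target with a wider denominator: "Among patients randomized to DSD, proportion that received DSD (target > 80" (per cent).

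**Its stated role.** Section 6.2.1 says of the measures other than the main one: "Other feasibility objectives will evaluate cross-over". Section 7.4 describes the pilot's main purpose as to "determine timely inclusion and randomization, measure adherence to protocol and assess safety aspects".

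**The data.** CRF1 records "electrode placement for each defibrillation" (section 8.1, Prehospital CRF1). Section 14.3 has every defibrillator file analysed for the energy delivered at each shock. Section 6.3.4 provides for standard defibrillation when DSD cannot be carried out, and such patients stay in the ITT analysis.

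**The concern.** The intervention is a course of shocks, but the endpoint is one yes or no per patient. A patient given one DSD and then only single shocks counts the same as a patient given DSD throughout. Section 6.2.1 also counts only VF at the next rhythm analysis, whereas sections 2.2 and 6.6 apply the strategy to VT/VF and to all later shocks. A patient in pulseless VT at that analysis therefore drops out of the denominator.

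The pilot is meant to show that the strategy can be delivered and to inform the sample size of a survival trial. If DSD is started but often not continued, the contrast between the arms in that trial will be smaller than the adherence figure suggests, and no listed endpoint would put a number on the gap.

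**Working it through.** **1. The plan's own figure.** Section 6.3.3 plans 40 patients at 3:1. 40 × 3/4 = 30 DSD and 40 × 1/4 = 10 standard, as stated. The protocol gives no power calculation, and the 80% target is a chosen threshold, so there is nothing further to reproduce.

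**2. What the target requires.** It needs the smallest whole number of patients above 80% of the denominator:

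| Patients in denominator | Needed for > 80% |
|---|---|
| 30 | 25 (83.3%) |
| 25 | 21 (84.0%) |
| 20 | 17 (85.0%) |
| 15 | 13 (86.7%) |

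**3. Two readings of the numerator.** The protocol does not say whether receiving DSD means at any time or at the next rhythm analysis. The second reading excludes a late first DSD. On both, a crew that gives DSD at that analysis and single shocks afterwards is a success, so the gap does not depend on the reading.

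**4. Reversion, by count.** Assume all 30 DSD-arm patients are in the denominator, all receive a first DSD, and all have later VT/VF shocks. Let k be the number whose crews revert. The endpoint as written is 30/30 = 100% for every k. The proportion with DSD at every shock is (30 − k)/30:

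| k reverting | As written | DSD at every shock |
|---|---|---|
| 5 | 100% | 83.3% |
| 6 | 100% | 80.0% (not > 80%) |
| 10 | 100% | 66.7% |
| 15 | 100% | 50.0% |
| 30 | 100% | 0% |

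**5. Reversion, by shock.** Assume instead that each patient has a first DSD and m = 2 later shocks, each given as DSD with probability q, independently. The expected proportion of patients with DSD throughout is q². The expected share of shocks given as DSD is (1 + 2q)/3. The chance that at least 25 of 30 patients have DSD throughout is a binomial tail with probability q²:

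| q | All shocks DSD | Share of shocks DSD | Chance of ≥ 25/30 | Chance as written |
|---|---|---|---|---|
| 0.7 | 49% | 80.0% | 0.0001 | 1 |
| 0.8 | 64% | 86.7% | 0.018 | 1 |
| 0.9 | 81% | 93.3% | 0.48 | 1 |

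The per-patient and per-shock summaries differ widely, so both are worth reporting.

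**6. Where to start counting.** Suppose 20 patients are eligible, 10 never get second pads and 10 get DSD throughout. The present endpoint reads 10/20 = 50%. A per-shock measure that starts at second-pad attachment sees only the second 10 patients and reads 100%. Started at randomization, with equal numbers of shocks per patient, it reads 50%. Counting must therefore start at randomization.

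**The case against.** The endpoint does the job section 6.2.1 gives it. These measures are presented as cross-over, and the two arms have mirrored per-patient counts of who received DSD. That is a conventional choice and contradicts neither section 2.2 nor section 6.6. This stands, and it is why the endpoint should be kept.

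The exact counting rule may be in a statistical analysis plan that is not shown. That is possible, but the protocol itself fixes the unit, denominator and target, and none of them reaches later shocks.

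Four stronger readings are tempting, and the documents do not support them:

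- A reader might infer that the protocol calls such patients fully adherent. It does not; it only counts them as having received DSD.
- A reader might infer that most DSD-arm shocks could be single. With 20 patients, 3 indicated shocks each and universal reversion, 20/60 = 33% of shocks would follow allocation. That is an arithmetic worst case on assumed numbers. Crew training (section 2.6) and the instruction in section 6.6 point away from it.
- A reader might infer that reversion would go unseen. Section 4.5 provides case-by-case assessment and feedback, and shock-level data are collected. What is missing is a summary measure.
- A reader might infer that every single shock in the DSD arm is a crew failure, or that every recurrence of VF calls for DSD. Section 6.3.4 provides for standard shocks when DSD cannot be done, and section 6.6 runs only until ROSC, so recurrence after ROSC is not clearly covered.

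**Conclusion.** The point holds as a gap in measurement. The > 80% target tests whether DSD was given. It says nothing about whether DSD was sustained, which sections 2.2 and 6.6 require and which the adherence purpose in section 7.4 needs. On the assumptions in the working, reported adherence can be 100% while the proportion of patients with DSD at every shock lies anywhere from 0% to 100%. The two measures fall on opposite sides of the target once 6 of 30 crews revert. The number of later shocks, the reversion rates and the independence between shocks are assumptions, so the actual gap cannot be estimated from the protocol.

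Two smaller defects in the same endpoint also stand. Section 6.2.1 says VF where the strategy says VT/VF, and the Synopsis uses all patients randomized to DSD as the denominator where section 6.2.1 uses a subset.

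**What to change.** 1. Keep the present endpoint and its > 80% target, labelled as the initiation (cross-over) measure. Write VT/VF for VF in its denominator, and use one denominator in both the Synopsis and section 6.2.1.
2. Add a sustained-adherence measure. The denominator is DSD-arm patients with at least one VT/VF shock after randomization and before the strategy's stated end. Report the share of all such shocks given as DSD, and the proportion of patients in whom all such shocks were DSD.
3. Count from randomization, so that patients whose second pads were never attached count as non-adherent.
4. Report separately the shocks given before the pads could be attached and the standard shocks given under section 6.3.4.

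**Cost.** Endpoint wording and a little more analysis; no treatment rule changes. CRF1 and the defibrillator files already hold the shock-level data. The CRF1 content listed in section 8.1 does not mention a reason for withholding DSD, so item 4 may need one more field if the reason is not captured elsewhere. Sustained adherence may read lower than the initiation figure.
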